6.2 Administration of ¹³C-Spirulina GEBT

Administer the ¹³C-Spirulina GEBT to participants according to the instructions enclosed in the GEBT kit in the approved package insert and modified labeling under the supervision of a Cairn telehealth administrator as described in SOP-CD-028, Telehealth Administration Procedures (Exhibit E).

6.3 Analysis of breath samples

Accession samples, analyze breath samples, and generate reports using Cairn's approved ABCA GIRMS instrument according to SOP-CD-005, Breath Test Processing. Patient reports from ¹³C-Spirulina GEBT administered according to telehealth procedures will NOT be provided to participants or referring clinicians prior to FDA approval of telehealth procedures.

6.4 Experimental Design and Analyses

6.4.1 Study population

The current intended use population for ¹³C-Spirulina GEBT is adults, symptomatic for gastroparesis. A recent US study Syed et al., 2020 determined an overall prevalence of gastroparesis at ~0.16%. In this study, over 70% of patients diagnosed with gastroparesis were also diabetic – with the majority (~55%) comprising Type II diabetics. In addition, ~66% of patients diagnosed with gastroparesis were women. Almost 69% of gastroparetic patients were aged 50 or above. It has been shown that there is a correlation between incidence of diabetes and level of education (Borrell et al., 2006), therefore it might be expected that a significant proportion of the intended use population for ¹³C-Spirulina GEBT may have no more than a high school level of education. In order for GEBT to be able to be successfully administered via telehealth, it must therefore be demonstrated to be usable for subjects without a college education and for older subjects, who may not have the degree of familiarity with technology that might be expected from younger subjects.

In order to ensure that the study is representative of the intended use population and of a range of expected abilities, experience and understanding of the technology and procedures required for telehealth administration of GEBT, this study will include a minimum of 15 subjects each in the following subgroups (subjects may fall into more than one subgroup):

- Subjects symptomatic for gastroparesis
- Subjects aged 55 or older

- Subjects with no more than a high school education

6.4.2 Tasks and Use Scenarios

GEBT is typically administered on a single occasion and subjects administered the test by telehealth would not be expected to become experienced in its use. Therefore, usability testing will be performed where subjects are administered the GEBT via telehealth on a single occasion, and where the subjects have never previously taken a GEBT (in office) and have no prior experience of collecting breath samples.

6.4.3 Instructions for Use

GEBT kits for use via telehealth will be the same as GEBT kits for use in office. However, additional labeling (Patient Information Sheet) will be provided with GEBTs shipped to a subject's home for administration under telehealth supervision. Copies of this labeling can be found in Exhibit F. Additional instructions for use are not needed for GEBT administered via telehealth, because a healthcare professional, trained in test administration, will remotely supervise the self-administration of the GEBT.

6.4.4 Participant Training

Participants in this study who are taking the GEBT at home, under supervision of a telehealth professional will receive no prior training in how to administer the GEBT, in the same way that patients that would be administered the GEBT via telehealth would not have had prior training. Telehealth administrators, who are Cairn employees, will be trained on telehealth administration procedures (SOP-CD-028, Exhibit E) according to standard Cairn training policies. A minimum of two and up to four different individuals trained in telehealth procedures will administer the GEBT by telehealth for this study.

6.4.5 Safety of telehealth administration of ^{13}C -Spirulina GEBT

Preliminary risk analysis of the telehealth administration procedure did not identify any increased risks of adverse events associated with telehealth administration of the GEBT compared with in-office administration of the test. This usability study will confirm that there is no more than expected frequency of adverse events during administration of GEBT by a telehealth professional, than would be expected during administration of GEBT in a clinician's facility.

6.4.5.1 Cairn's medical director will review individual adverse events reported during the study to determine whether the adverse events would have been more or less likely to occur during test administration in a physician's office.

6.4.6 Patient ability to prepare and administer the ^{13}C -Spirulina GEBT, under the supervision of a telehealth professional, according to instructions

Ability to prepare GEBT will be assessed by the telehealth administrator's observation of the patient and by a patient questionnaire (Exhibit B) regarding the GEBT that will be completed at the end of the test and returned to Cairn along with the test request form and breath samples.

6.4.6.1 The patient will be asked whether the meal preparation instructions were clear and whether the instructions on meal preparation could be improved upon (Exhibit B).

6.4.6.2 The telehealth administrator will observe and record the following (Exhibit C):

- Was the patient able to transfer the meal to the cooking cup without significant spills?
- Did the patient remove the oxygen absorber?
- Did the patient add the correct amount of water to the meal?
- Did the patient cook the egg for the correct length of time?
- Did the patient flip the egg in the middle of cooking?
- Did the egg appear to be adequately cooked?

6.4.7 Patient ability to complete the GEBT test request form, under the supervision of a telehealth professional, according to instructions

Ability to complete the GEBT test request form will be assessed by Cairn accessioning personnel upon receipt of returned breath samples and by a patient questionnaire (Exhibit B) that will be completed at the end of the GEBT.

6.4.7.1 The patient will be asked whether the test request form was easy to complete (Exhibit B)

6.4.7.2 Accessioning personnel will evaluate the returned test request form and breath samples as follows (Exhibit D).

- Was the test request form returned to Cairn in the mailer with the breath samples?
- Was the patient demographic information (including units) entered correctly on the form?
- Were pre-meal breath sample collection times recorded appropriately?
- Were meal start/end times recorded appropriately?
- Were post-meal breath sample planned and actual sample collection times calculated/recorded appropriately?

6.4.8 Patient ability to collect GEBT breath samples under the supervision of a telehealth professional

Ability to collect GEBT breath samples will be assessed by examination of GEBT results for participants (ensure adequate CO_2 in each sample/delta values follow expected pattern if collected in correct order). In addition, patients will be asked about instruction on breath sample collection.

6.4.8.1 Patients will be asked whether instructions of collecting breath samples were easy to follow (Exhibit B).

6.4.8.2 Cairn Telehealth personnel will review breath samples over the telehealth platform and note whether condensate is observed in breath tubes (Exhibit C)

(Note: breath condensate is not always visible in breath tubes, even when a sample has been collected successfully, this data is being collected for information only)

6.4.8.3 Cairn Clinical Laboratory personnel will review breath tubes received and GEBT results obtained to determine whether breath samples were collected correctly as follows (Exhibit D):

- Is condensate visible in breath tubes (see note above)?

- Does each breath sample contain a minimum of 1%CO₂ (in the case of pre-meal samples, at least one sample must contain a minimum of 1% CO₂)?
- Did the breath samples appear to have been collected in the correct order? (In correctly collected samples sets, pre-meal sample delta values will (usually) be more negative than post-meal delta values and post-meal delta values tend to increase in value over time – in normal patients, they may start to decline after 120 minutes – and in delayed patients rise to a maximum at 240 minutes).

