6.0 STUDY PROCEDURES/RESEARCH METHOD

6.1 Study Scheme

Visit 1: For each potential participant, perform a screening visit at the clinical study site or via the telehealth communications platform where the study is explained to the participant. Ensure that the participant is eligible to participate in the study. Answer any questions about the GEBT test procedure and ask the participant to provide consent to participate in the study (see SPEC-CD-036). The informed consent form will be signed in the presence of the research coordinator explaining the consent form. A copy of the signed consent form will be sent via fax, scan or email for the research coordinator to sign and return to the participant. Participants are free to leave the facility or log out upon completion of the screening visit.

Visit 2: Within two weeks of visit 1, participants will log into the telehealth platform using the information provided by a Cairn telehealth administrator at which time the GEBT will be administered under virtual supervision. After confirmation that the participant has met the fasting and dietary restriction requirements, the participant will begin to complete the test request form, provide baseline (PRE-meal) breath samples, prepare the GEBT test meal, consume the prepared GEBT test meal, and collect post meal breath samples at 45, 90, 120, 150, 180 and 240 minutes after consumption of the meal under the supervision and instruction of a Cairn telehealth administrator.

Visit 3: Follow up contact (e.g. phone call, email, in-person, etc) will be made with the participant within one week following the GEBT administration to assess whether there were any post-administration adverse events and to administer a patient questionnaire to complete the subject's participation in the study.

Table 3. Schedule of Activities (SoA)

Procedure	Screening (Visit 1)	Visit 2	Follow-up (Visit 3)	Notes
Informed Consent	X			
Inclusion and exclusion criteria	X			
Telehealth administration of ¹³ C-Spirulina GEBT		X		
Completion of post-test questionnaire			X	
AE review			X	
SAE review			X	

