6.4.9 Ability to successfully ship kits/breath samples to/from home

Ability to ship GEBT kits/breath samples to/from home will be assessed by surveying patients regarding shipping (Exhibit B) and by recording the dates that kits were shipped and received.

6.4.9.1 Patients will be asked whether they have any problems receiving their GEBT kit (Exhibit B)

6.4.9.2 Patients will be asked whether they had any issues returning breath samples to Cairn (Exhibit B)

6.4.9.3 Cairn personnel will record dates when each kit and breath samples are shipped/received.

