15.0 EXHIBITS

- A. FDA's public announcement of PMA approval of ^{13}C -Spirulina GEBT and a copy of PMA 110015 Gastric Emptying Breath Test Letter of Approval

- B. Telehealth Administration of ¹³C-Spirulina Gastric Emptying Breath Test (¹³C-GEBT) Usability Study – Patient Questionnaire to be completed at end of ¹³C-Spirulina GEBT
- C. Telehealth Administration of ¹³C-Spirulina Gastric Emptying Breath Test (¹³C-GEBT) Usability Study – Telehealth Administrator Patient Ability/Compliance Questionnaire
- D. Telehealth Administration of ¹³C-Spirulina Gastric Emptying Breath Test (¹³C-GEBT) Usability Study – Test Request Form and Breath Sample Evaluation
- E. SOP-CD-028, Telehealth Administration Procedures
- F. SPEC-CD-032, Patient Preparation Sheet

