5.0 MEAL PREPARATIONWere the meal preparation instructions clear? Yes No

If no, please share any ideas on how to clarify the process: _____

6.0 TELEHEALTH PLATFORMWas the video link during the test easy to use? Yes No

If no, please describe what was difficult to use: _____

Was texting communication easy to understand? Yes No Did you lose internet connection at any point during the test? Yes No

What kind of internet connection were you using for the telehealth administration of GEBT?

Cable DSL Satellite Cellular Other (Describe: _____) Don't know **7.0 SAMPLE SHIPPING**Was it easy to return breath samples to Cairn? Yes No

If no, please describe what was difficult about the shipping of breath samples?: _____

Form Completed by: _____ Signature: _____ Date: _____

Patient ID: _____

GEBT ID: _____

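### The protocol gives the single patient questionnaire two incompatible times and return routes, and under one of them the return-shipping item is answered before the samples are shipped

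*Protocol*

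**What the plan says.** Three places in the protocol put the questionnaire on the day of the test:

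- Section 6.4.6 has it "completed at the end of the test and returned to Cairn along with the test request form and breath samples".
- Section 6.4.7 says the test request form will be assessed in part "by a patient questionnaire (Exhibit B) that will be completed at the end of the GEBT".
- The exhibit list in section 15.0 titles Exhibit B as a "Patient Questionnaire to be completed at end of" the GEBT.

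Three places put it at follow-up:

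- Section 6.1 describes Visit 3 as a contact that "will be made with the participant within one week following the GEBT administration", used to ask about adverse events and "to administer a patient questionnaire to complete the subject's participation in the study".
- Table 3 has one questionnaire row, marked at Visit 3 and blank at Visit 2.
- Section 6.6, in defining when a participant has completed the study, names the questionnaire as a follow-up item.

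On shipping, section 6.4.9.2 states: "Patients will be asked whether they had any issues returning breath samples to Cairn", and points to Exhibit B. The matching item is Exhibit B section 7.0: "Was it easy to return breath samples to Cairn", with a free-text follow-up on what was difficult.

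**The concern.** A questionnaire that travels with the breath tubes has to be finished before the tubes are sent. The item on returning the samples is worded in the past tense, about something that has not yet happened. The participant can comment on packing, but not on reaching a drop-off point, on pickup, or on delay. Those are the difficulties that a home-return survey is there to find. A participant who never ships would also send back no form.

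Apart from that item, staff cannot tell from the protocol whether the form is self-completed on the day or administered by contact up to a week later. At stake are the validity of one stated shipping assessment and the consistency of how the form is collected.

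**Working it through.** The point rests on no sample size, power or error-rate figure, so the check is a comparison of the text.

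**1. Is it one form or two?** Section 15.0 lists one patient questionnaire, Exhibit B. Exhibits C and D are completed by the telehealth administrator and by Cairn accessioning and laboratory personnel. Table 3 has one questionnaire row. Nothing supports a second patient questionnaire.

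**2. Can the two instructions be reconciled?**

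| Feature | 6.4.6, 6.4.7, Exhibit B title | 6.1, Table 3, 6.6 |
|---|---|---|
| Time | End of the test (Visit 2) | Follow-up contact, up to 7 days later (Visit 3) |
| Mode | Completed by the patient | Administered by contact (phone, email, in person or similar) |
| Return | With the request form and tubes (6.4.6) | None stated in 6.1 or Table 3 |

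They could coincide only if the participant kept the package until the follow-up contact. SOP-CD-028 section 3.6.2 points the other way: the administrator encourages shipping within 3 days.

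**3. Does the form precede shipping under 6.4.6?** The kit holds one pre-labeled mailer (Table 1). The test request form goes in it with the tubes (section 6.4.7.2 and SOP section 3.6.2). A questionnaire returned along with both is, by close inference, in that same mailer, although 6.4.6 does not say so outright. SOP section 3.6.6 treats drop-off as a later step, with the confirmation text scheduled for the day after packaging. Under this route every section 7.0 answer comes before hand-over to the carrier.

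**4. Does the SOP settle the matter?** No. Its closing-call checklist puts the test request form in the mailer and does not mention the questionnaire.

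**5. What depends on the affected item?**

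- 6.4.9.2 (return problems) depends on it directly.
- 6.4.9.1 (kit receipt, Exhibit B section 2.0) does not: receipt is past at either time.
- 6.4.9.3 (dates shipped and received) does not: Cairn personnel record these.
- 6.5.6 (shipping acceptance criterion) does not: it uses kit delivery in time for the test and return and analysis within 28 days.
- 6.5.3 (at least 90% of questionnaires without meal-preparation issues) does not: the meal is over before either candidate time.

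**The case against.** The strongest reply is that the conflict has little consequence. Most of it stands.

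- **Lost failures.** A reader might infer that participants who fail to ship disappear from view. They do not. The 6.4.9.3 dates show non-return. SOP sections 3.6.6 to 3.6.8 send a next-day text, call anyone who replies no, and log receipt. The participant's written account may be lost, but not the failure.
- **Uninformative shipping survey.** A reader might extend the fault to everything asked under 6.4.9. The kit-receipt item is sound under either timing. Only section 7.0 is exposed, and only if 6.4.6 is the instruction followed.
- **Threat to the 90% criterion.** At the minimum of 30 participants the limit is 27/30 = 90%, and one form is worth 1/30 = 3.3 percentage points (1/50 = 2 points at 50 participants). Losing one favourable form from a result exactly at the limit gives 26/29 = 89.7%. That is the granularity of a small study. The documents do not show that timing or mode changes the meal-preparation answers, or that both modes will be used. Pooling of modes is a possible result of the ambiguity, not a stated plan.

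What the reply does not remove is the contradiction itself. The protocol fixes time and return route in two incompatible ways, so this is not a detail left to an analysis plan.

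**Conclusion.** The protocol contradicts itself on when and how Exhibit B is completed, and no passage resolves it. Under the 6.4.6 route, all answers to section 7.0 predate the event they describe, so 6.4.9.2 cannot be met as intended for drop-off and return. Under the Visit 3 route the item can work, provided the samples have been sent by then.

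The size is small: one yes/no item with its free-text follow-up, in a study of 30 to 50 participants. Neither the 6.5.6 nor the 6.5.3 criterion is shown to be invalidated. The conclusion assumes that Exhibit B is the only patient questionnaire and that it travels in the single kit mailer. The first follows from section 15.0 and Table 3. The second is a close inference from 6.4.6 and the kit contents.

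**What to change.** 1. State one time and one mode for Exhibit B, and make 6.1, Table 3, 6.4.6, 6.4.7, 6.6 and the Exhibit B title agree.
2. Whatever is chosen for the rest of the form, ask section 7.0 at the Visit 3 contact. Ask it of every participant, whether or not samples have been received, and record shipping status at that contact. The window in 6.1 has no earliest day, so some participants may not yet have shipped.
3. In 6.4.6, delete the instruction that the questionnaire is returned with the request form and samples, at least for section 7.0.

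Do not make the item wait for confirmed sample receipt. That would again miss participants who never ship, and it could run past the one-week Visit 3 window, since 6.5.6 allows up to 28 days for return and analysis.

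Visit 3 is already planned, so no new contact is needed. The cost is a minor protocol amendment, which section 12.1 requires to have IRB approval before it takes effect.

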6.4.9 Ability to successfully ship kits/breath samples to/from home

Ability to ship GEBT kits/breath samples to/from home will be assessed by surveying patients regarding shipping (Exhibit B) and by recording the dates that kits were shipped and received.

6.4.9.1 Patients will be asked whether they have any problems receiving their GEBT kit (Exhibit B)

6.4.9.2 Patients will be asked whether they had any issues returning breath samples to Cairn (Exhibit B)

6.4.9.3 Cairn personnel will record dates when each kit and breath samples are shipped/received.

6.4.10 Ability of a telehealth platform to function correctly

Telehealth platform software will be validated in a separate protocol. However, this study will verify that the software is user friendly and not subject to frequent failures during use.

6.4.10.1 Patients will be asked whether they had trouble using the telehealth platform and whether their internet connection failed during the test (Exhibit B).

6.4.10.2 Telehealth administrators will be asked whether the patient had trouble using the telehealth platform and whether the software/their internet connection failed during the test (Exhibit C)

6.5 Acceptance Criteria for Demonstration of Usability of the Telehealth Administration

6.5.1 Study population

Study includes a minimum of 15 subjects each in the following subgroups (subjects may fall into more than one subgroup):

- Subjects symptomatic for gastroparesis
- Subjects aged 55 or older
- Subjects with no more than a high school education

6.5.2 Safety of telehealth administration of ^{13}C -Spirulina GEBT

There are no more/more severe adverse events than would have been expected to occur during in-office administration of ^{13}C -Spirulina GEBT.

6.5.3 Patient ability to prepare and administer the ^{13}C -Spirulina GEBT, under the supervision of a telehealth professional, according to instructions

Greater than or equal to 90% of Patient questionnaires record no issues with meal preparation (Exhibit B, Section 4)

Greater than or equal to 90% of meal preparation steps (described in Exhibit C, section 1) were completed successfully.

6.5.4 Patient ability to complete the GEBT test request form, under the supervision of a telehealth professional, according to instructions

Errors in test request forms occur at a rate of ~16% for in-office test administration. There are no more errors in test request form completion than are routinely found in test request forms returned with GEBTs administered in office.

6.5.5 Patient ability to collect GEBT breath samples under the supervision of a telehealth professional

Missing breath samples occur at a rate of ~6% for in-office test administration. There is not a higher incidence of missing breath samples in breath samples collected via telehealth than are routinely found in breath samples returned from GEBTs administered in office.

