5.0 SUBJECT SELECTION

Cairn personnel and their family and friends may volunteer to be a participant in this study provided they are not familiar with the GEBT test administration procedure and have never been administered a GEBT test.

Participants may also be recruited from gastroenterology, multi-disciplinary, primary care or clinical research practices knowledgeable and experienced in the evaluation and treatment of patients suspected of gastroparesis (intended use population for GEBT). Participants should not have previously undergone a gastric emptying breath test.

This study requires a minimum of thirty (30) and up to fifty (50) participants. Of the participants required for this study, at least fifteen (15) must be symptomatic for gastroparesis, at least fifteen (15) must be over the age of 55, and at least fifteen (15) must have no higher than a high school education or equivalent.

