6.6 End of Study

- Participants may withdraw from the study at any time, without prejudice
- An authorized investigator may discontinue any test subject at any time if medically indicated or in the best interest of the individual
- Participants who do not complete all components of the testing and compliance procedures will be excluded from the statistical analysis
- Withdrawn participants may be replaced to achieve the number of subjects specified
- The trial may be terminated prematurely if, in the judgement of Cairn's Medical Director, the severity or frequency of adverse events so warrants

Each participant is considered to have completed the study when they have completed the GEBT test administrations, follow-up questionnaire and AE review follow-up and all collected breath samples have been analyzed on the ABCA GIRMS system.

The end of the study is defined as the date on which all of the participants' breath samples have been analyzed on the ABCA GIRMS, all participant's study questionnaires have been returned, and all follow-up (AE review) has been completed.

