11.4 Statistical Analysis

Comparisons of rates of occurrence of errors in test administration procedures between telehealth and in-office administered tests will be performed according to accepted statistical techniques.

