3.0 TELEHEALTH PLATFORM

Did the patient appear to have trouble using the telehealth platform? Yes No

If no, please describe what was difficult to use: _____

Did the telehealth session fail at any time during your test? Yes No

If yes, please explain: _____

Did you lose internet connection at any point during the test? Yes No

What kind of internet connection were you using for the telehealth administration of GEBT?

Cable DSL Satellite Cellular Other (Describe: _____) Don't know

Patient ID: _____

GEBT ID: _____

1.0 TEST REQUEST FORMWas the completed test request form returned with the GEBT breath samples? Yes No Was patient height recorded? Yes No Units entered? Yes No Was patient weight recorded? Yes No Units entered? Yes No Was patient sex recorded? Yes No Was patient age recorded? Yes No Were the pre-meal breath sample collection times entered? Yes No Was the meal start time entered? Yes No Was the meal end time entered? Yes No Were all post-meal planned breath sample collection times calculated correctly? Yes No Were all post-meal actual breath sample collection times entered? Yes No

Post-meal collection time	Post meal planned collection time	Post meal actual collection time	Actual time +/- 5 mins of planned time?
45 minutes	Yes  No 	Yes  No 	Yes  No 
90 minutes	Yes  No 	Yes  No 	Yes  No 
120 minutes	Yes  No 	Yes  No 	Yes  No 
150 minutes	Yes  No 	Yes  No 	Yes  No 
180 minutes	Yes  No 	Yes  No 	Yes  No 
240 minutes	Yes  No 	Yes  No 	Yes  No 

2.0 BREATH SAMPLE COLLECTIONWas condensate visible in the breath tubes received? Yes No Did the breath samples contain sufficient CO₂ (i.e., >1% CO₂)

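### Sections 6.5.4 and 6.5.5 set zero-margin limits against approximate in-office rates with no counting unit, so a truly equal procedure often fails; the 6.6 exclusion may remove the events being counted

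*Protocol*

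**What the plan says.** Section 6.5 of the protocol lists the acceptance criteria for usability. Section 6.5.4 gives the reference for forms, "Errors in test request forms occur at a rate of ~16% for in-office test administration", and then the rule, "There are no more errors in test request form completion than are routinely found in test request forms returned with GEBTs administered in office". Section 6.5.5 does the same for samples: "Missing breath samples occur at a rate of ~6% for in-office test administration", followed by "There is not a higher incidence of missing breath samples in breath samples collected via telehealth" than is usual in office. Neither section states a margin, a maximum count or a confidence limit. Neither says whether the percentage refers to forms or single entries, or to tests, time points or tubes.

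On sample size, Section 5.0 says "This study requires a minimum of thirty (30) and up to fifty (50) participants". Section 11.4 says that comparisons of error rates with in-office testing "will be performed according to accepted statistical techniques".

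Section 6.6 adds "Participants who do not complete all components of the testing and compliance procedures will be excluded from the statistical analysis". The same section later defines a completed participant by the test administration, the questionnaire, the adverse-event follow-up and analysis of the samples that were collected. It does not mention all the samples that were scheduled.

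**The concern.** A rule that allows no excess over a reference rate, applied to the observed rate in a small single-arm study, is close to a coin toss when the true rate equals the reference. The sponsor could have a sound procedure and miss a criterion by chance. Section 6.5.3 sets numerical thresholds of at least 90%, so the protocol fixes cut-offs where it chooses to.

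The unit matters just as much. A 6% rate per test and a 6% rate per tube are very different findings. For forms, the evaluation sheet in Exhibit D holds many separate boxes, including one headed "Actual time +/- 5 mins of planned time", so the share of forms with any error depends on which boxes count.

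The exclusion in 6.6 works in the other direction. Returning every sample and a full form is plausibly part of completing the test. If so, the participants who fail are the ones who leave the analysis, and the criterion passes because of the exclusion. The synopsis intends to conclude that telehealth is comparable with in-office testing, so both faults bear on a stated aim.

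**Working it through.** **Inputs.** n = 30 to 50 (Section 5.0). In-office rates p0 = 0.16 for forms (6.5.4) and 0.06 for missing samples (6.5.5). Eight tubes per test: two pre-meal and six post-meal (Table 1). The protocol derives no figure for these criteria, so there is none to reproduce. Assumptions: independent participants, and the in-office rates taken as exact.

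**1. Literal rule, participant as unit, true rate equal to in-office.** The largest passing count is c = floor(p0 × n), and P(pass) = P(X ≤ c), with X binomial(n, p0).

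| Criterion | n=30 | n=50 | all n from 30 to 50 |
|---|---|---|---|
| Forms, 16% | c=4, 46.3% | c=8, 59.3% | 43% (n=31) to 59% (n=50, among others) |
| Missing samples, 6% | c=1, 45.5% | c=3, 64.7% | 40% (n=33) to 67% (n=34) |

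One cell by hand: for missing samples at n=30, 0.94^30 + 30 × 0.06 × 0.94^29 = 0.156 + 0.299 = 0.455.

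Reading the approximate sign generously at n=30, so that 5/30 (16.7%) and 2/30 (6.7%) still pass, gives 65% and 73%. The problem is softened but not removed.

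**2. Literal rule, tube as unit.** With eight independent tubes per test there are 240 tubes at n=30 (c=14) and 400 at n=50 (c=24). P(pass) at a true 6% is 53% and 55%.

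**3. If a criterion were judged by whether telehealth is significantly higher.** Section 11.4 does not state this. Assume an exact one-sample test at one-sided 5%, with non-significance counted as a pass.

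| Unit and true rate | largest passing count, n=30 / n=50 | P(pass), n=30 / n=50 |
|---|---|---|
| Missing samples per participant, 6% (equal) | 4 / 6 | 97% / 97% |
| Missing samples per participant, 12% (doubled) | 4 / 6 | 71% / 61% |
| Missing samples per independent tube, 12% (doubled) | 21 of 240 / 32 of 400 | 7% / 0.6% |
| Forms per participant, 32% (doubled) | 8 / 12 | 34% / 14% |

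The same sentence in 6.5.5 therefore gives a weak or a strong safeguard depending on a unit that it does not state.

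**4. The exclusion in 6.6.** Suppose that every participant with a missing sample is treated as not having completed all components. The analysed set then has no missing samples, the observed rate is 0%, and 6.5.5 passes whatever the true rate. If completion refers only to the samples that were collected, such participants stay in and nothing is lost. Both readings can be drawn from 6.6.

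**5. What 30 to 50 participants can exclude.** Using the exact one-sided 95% upper limit per participant, excluding a 12% missing-sample rate needs 0 events in 30 (limit 9.5%; 1 in 30 gives 14.9%) or at most 1 in 50 (limit 9.1%; 2 in 50 gives 12.1%). At a true 6% the chance of this is 0.94^30 = 16% at n=30, and 0.94^50 + 50 × 0.06 × 0.94^49 = 0.045 + 0.145 = 19% at n=50.

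**The case against.** Test, significance level and analysis set are commonly left to a statistical analysis plan, and one may exist that is not shown. That stands against any criticism of Section 11.4 for being brief. It does not answer 6.5.4 and 6.5.5, where the protocol itself writes the pass rule.

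A reader might infer that the criteria usually let a doubled missing-sample rate through. The documents do not support that. It needs the participant as unit and a rule that non-significance means success, and the protocol states neither. The wording of 6.5.5 can be read per sample, and then a doubling is usually detected. With tubes correlated within a person (assumed intraclass correlation 0.3 to 0.5, normal approximation), a doubled rate still passes less than half the time: about 34–44% at n=30 and 19–30% at n=50. The per-test reading is arguably more natural, since 6% per independent tube implies that 1 − 0.94^8 = 39% of tests lack a tube, but the text does not settle it.

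A reader might also infer that 6.6 certainly empties 6.5.5 of its events. The completion sentence speaks of collected samples, so a participant with one missing tube may count as a completer. The exclusion bullet is worded differently, and the ambiguity remains.

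Finally, the protocol does not say outright that both criteria must be met, so no joint pass probability is relied on here.

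**Conclusion.** The concern holds in a limited form. Read as written, 6.5.4 and 6.5.5 fail an equal procedure about 41–57% of the time for forms and 33–60% for missing samples over n = 30 to 50, counted per participant, and missing samples fail about 45–47% of the time per independent tube at n=50 and n=30. This part does not depend on 11.4.

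The performance of a significance-test reading depends on the unit. A non-significant result could support a claim of comparability only if unit and rule are fixed beforehand.

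The conflict between 6.6 and 6.5.5 is real but conditional on what completion means. In the extreme reading, 6.5.5 cannot fail.

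The figures assume independent participants and in-office rates known exactly; the protocol gives no denominators for the 16% and 6%. The sponsor should correct this before results are seen.

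**What to change.** 1. In 6.6, state that every participant who starts the test stays in the denominators of 6.5.4 and 6.5.5, and that a missing sample or an incomplete form is an event and not a ground for exclusion. Reconcile the exclusion bullet with the completion sentence.
2. In 6.5.4 and 6.5.5, state one counting unit for each criterion and restate the in-office rates in that unit. Say whether the timing boxes in Exhibit D count as form errors, and whether one adequate pre-meal tube is enough, as 6.4.8.3 allows.
3. Report each telehealth rate with its exact one-sided 95% upper limit. Judge it against a ceiling that the sponsor justifies before results are seen, and say that 11.4 refers to this rule. Limit the conclusion to excluding rates above that ceiling, in place of a claim of no more errors than in office or of comparability.

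The cost is protocol wording, a recount of the two in-office rates and two confidence limits. No participants are needed beyond the present maximum, although the limits are tighter at 50 than at 30. The downside is a weaker claim: counted per participant, 30 to 50 people cannot usefully exclude a doubled missing-sample rate, as step 5 of the working shows. The choice of ceiling is left to the sponsor.
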